9.3.5 Hospitalization

In the absence of an AE, the Investigator should not report hospitalization or prolongation of hospitalization. This is the case in the following situations:

- Hospitalization or prolongation of hospitalization is needed for a procedure required by the protocol.
- Hospitalization or prolongation of hospitalization is part of routine procedure followed by study center.
- Hospitalization for survey visits or annual physicals.

In addition, a hospitalization for elective procedures planned before or after the start of the study for a pre-existing condition that has not worsened does not count as an SAE.

9.3.6 Serious Adverse Event Reporting

9.3.6.1 Governing Regulatory Requirements

Compliance with this request for prompt reporting is essential in that the sponsor is responsible for informing the US Food and Drug Administration (FDA) as well as all other participating Investigators of the event.

Under FDA ruling (US Code of Federal Regulations, Title 21 CFR Part 312.32) and the Guidance for Industry and Investigators Safety Reporting Requirements for INDs and Bioavailability/Bioequivalence studies, the sponsor is required to submit written documentation, in the form of an IND safety report, detailing:

• Any event associated with the use of the drug, that is both serious and unexpected, or

Page 63 of 99

• Any findings from clinical, epidemiological, or pooled analysis of multiple studies or any findings from animal or *in vitro* testing that suggest a significant risk in humans exposed to the drug.

Written submission must be made by the sponsor to the FDA and the IRB/IECs as soon as possible and in no event later than 15 calendar days after the sponsor's initial notification of the event. Any unexpected death or life-threatening suspected adverse drug reaction must be reported to FDA no later than 7 calendar days after the sponsor's initial receipt of the information. The sponsor shall also inform all Investigators.

Time Frame for Reporting

Any death, SAE, pregnancy (including pregnancy of a partner), experienced by a subject while receiving or within 28 days of receiving study drug, regardless of relationship to study drug, or any death that occurs more than 28 days after receiving study drug, and is believed to be study drug-related, must be promptly reported (within 24 hours of the Investigator becoming aware of the event) by e-mail to the sponsor (or designee). The contact information for SAE reporting:

For medical questions contact the Kadmon Medical Monitor:
E-mail:
Phone:
For SAE reporting send the SAE form, pregnancy form, or follow-up within
24 hours of becoming aware:
Kadmon Pharmacovigilance
Email:
or
Fax:

In the event of a subject, or a subject's partner, becomes pregnant while on study, they will be monitored until the outcome of the pregnancy is known. The baby will continue to be monitored to 30 days after delivery. The data are reported on a pregnancy form within 24 hours of becoming aware.

Confidential and Proprietary

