1.3 BELUMOSUDIL NONCLINICAL EXPERIENCE

In vitro, belumosudil has demonstrated an impact on the T-helper 17 (Th17) and regulatory T cells (Treg)-immune responses as well as on the actin/myosin cytoskeletal network and collagen formation. In vivo, belumosudil has demonstrated efficacy in a variety of clinically relevant animal models of disease including chronic graft versus host disease (cGVHD), scleroderma, idiopathic pulmonary fibrosis (IPF), and other autoimmune diseases.

Good Laboratory Practice (GLP) compliant rat and dog general toxicology/toxicokinetic studies of acute, sub-chronic (1-and 3-month), and chronic (6-month rat and 9-month dog) duration have been completed. In addition, safety pharmacology (human ether-à-go go related gene [in vitro], central nervous system [rat], respiratory [rat], and cardiovascular [dog]), embryo-fetal toxicology [rat and rabbit], male/female fertility [rat]), genotoxicity, and phototoxicity studies have also been completed. The primary nonclinical toxicology finding at/near clinically relevant exposures were limited to changes in the cardiovascular (blood pressure lowering), hepatic (transaminitis, hypertrophy/increased organ weight, and cholestasis/inflammation), renal (increased blood urea nitrogen [BUN], tubular changes, pigmentation, intracellular protein droplets in the epithelium), gastrointestinal (decreased appetite), and hematopoietic/immunologic (anemia with regeneration and thymic/splenic lymphoid depletion) systems.

Belumosudil demonstrated embryo-fetal toxicity/teratogenicity as well as reduced male fertility (reduced fertility index/sperm concentration/motility and increased abnormal sperm percentage), and changes in the testes/epididymis (decreased organ weights and degenerative histopathology). Male fertility findings were generally at higher than clinically relevant exposures.

All pivotal non-clinical safety studies (i.e., those studies identified in International Conference on Harmonization guidelines as needing to be conducted in accordance with GLP) were conducted in a country that is a member of the Organisation for Economic Cooperation and Development (OECD) Mutual Acceptance of Data program in accordance with the OECD Test Guidelines and Principles of GLP. Study details and potential clinically relevant findings from these studies are summarized in the Belumosudil Investigator's Brochure.

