 - b. Sexually active women of childbearing potential enrolled in the study must agree to use 2 forms of accepted methods of contraception during the course of the study and for 3 months after their last dose of study drug. Effective birth control includes (i) IUD plus 1 barrier method; (ii) on stable doses of hormonal contraception for at least 3 months (e.g., oral, injectable, implant, transdermal) plus 1 barrier method; or (iii) two barrier methods. Effective barrier methods are male or female condoms, diaphragms, and spermicides (creams or gels that contain a chemical to kill sperm), or a vasectomized partner.
- 8. For male patients who are sexually active and who are partners of premenopausal women: agreement to use 2 forms of contraception as in Criterion Number 7 above during the treatment period and for at least 3 months after the last dose of study drug.
- 9. Male subjects must not donate sperm for 3 months after last dose of study drug.

10. Able to provide written informed consent prior to the performance of any study-specific procedures.

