6.2.5 Pregnancy Testing

Pregnancy tests (urine) will be done in women of childbearing potential. Positive urine results are to be confirmed with serum testing. In the event of a positive urine test at baseline, serum testing results should be acquired within 48 hours prior to study start.

In the event that a subject or subject's partner becomes pregnant while on study, they will be monitored until the outcome of the pregnancy is known. The baby will continue to be monitored to 30 days after delivery. The data are reported on a pregnancy form within 24 hours of becoming aware.

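### Mandatory pregnancy reporting ends 28 days after the last dose, while the contraception and sperm-donation rules run for 3 months: a low-severity gap in safety capture

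*Protocol*

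**What the plan says.** **Reporting.** Protocol 9.3.6.1 (time frame for reporting) lists among the events to be sent to the sponsor within 24 hours, whatever their relationship to study drug, any "pregnancy (including pregnancy of a partner), experienced by a subject while receiving or within 28 days of receiving study drug". The only event that this sentence carries past 28 days is death: "or any death that occurs more than 28 days after receiving study drug, and is believed to be study drug-related".

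**Follow-up.** Protocol 6.2.5 states: "In the event that a subject or subject's partner becomes pregnant while on study, they will be monitored until the outcome" is known, and the infant is then followed to 30 days after delivery. Section 9.3.6.1 repeats this. Section 3.1 gives the study 4 weeks of follow-up after dosing. The last scheduled visit and the last pregnancy test fall 28 ± 3 days after the last dose (section 5.5 and Appendix A).

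**Precautions against conception.** In Protocol 3.4, criterion 7b sets this rule for sexually active women of childbearing potential: "2 forms of accepted methods of contraception during the course of the study and for 3 months after their last dose of study drug". Criterion 8 asks the same of male subjects with premenopausal partners, "during the treatment period and for at least 3 months after the last dose of study drug". Criterion 9 adds: "Male subjects must not donate sperm for 3 months after last dose of study drug".

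**Named hazard.** Protocol 1.3 states: "Belumosudil demonstrated embryo-fetal toxicity/teratogenicity as well as reduced male fertility". It adds that the male fertility findings were generally seen above clinically relevant exposures. It attaches no such qualifier to the embryo-fetal finding.

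**The concern.** The protocol asks subjects of both sexes to avoid conception for 3 months after the last dose, but obliges sites to report a failure of that precaution only during the first 28 days. A pregnancy in a subject or partner that begins on day 45 or day 80 lies inside the contraception period. No section requires it to be reported, and none gives it the follow-up to outcome and to 30 days after delivery that a pregnancy a few weeks earlier would receive.

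What is at stake is complete safety information on a hazard that the protocol itself names. If late pregnancies surface only when something goes wrong and someone judges it possibly related, normal outcomes go uncounted and adverse ones have no denominator. Nothing in the efficacy analysis, the sample size or the planned safety tables depends on this.

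**Working it through.** The plan gives no figure of its own to reproduce. The check compares two stated durations and then asks whether any other section closes the difference.

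**Inputs**
- Pregnancy reporting window after the last dose: 28 days (Protocol 9.3.6.1).
- Contraception and sperm-donation period: 3 months for women and for sperm donation, at least 3 months for men with premenopausal partners (Protocol 3.4, criteria 7b, 8 and 9).
- Conversion of 3 months to days, M: not given. Assumed 84 to 92, with 90 as the central value.
- Timing of the last visit: 28 ± 3 days (Protocol 5.5).

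**Step 1. Uncovered share of the post-dose period = (M − 28) / M**

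| M (days) | Days not covered | Share |
|---|---|---|
| 84 | 56 | 66.7% |
| 90 | 62 | 68.9% |
| 91 | 63 | 69.2% |
| 92 | 64 | 69.6% |

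**Step 2. Allowing for the visit window.** Suppose that in practice capture ends at the last visit, on day 25 to 31. The share then runs from (84 − 31)/84 = 53/84 = 63.1% to (92 − 25)/92 = 67/92 = 72.8%. The uncovered part is the larger part under every conversion.

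**Step 3. Does another section close the gap?**
- *Section 9.1* asks that a known untoward event after the AE reporting period be reported if the investigator judges it possibly related. It is not limited to deaths or SAEs and has no end date. But it does not name pregnancy, it depends on a causality judgement, and it provides no means of learning of the event.
- *Section 9.3.6.2* makes possibly related SAEs reportable after 28 days. Congenital anomaly is a seriousness criterion in 9.3.1, so an affected infant would qualify if the site knew and judged it possibly related. Pregnancy is not among the criteria.
- *Section 9.4* requires follow-up of possibly related late SAEs until they resolve or are judged stable or irreversible. It does not address pregnancies.
- *Sections 6.2.5 and 9.3.6.1* tie follow-up to the time on study, which by section 3.1 ends about 4 weeks after dosing.

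These are partial backstops. None requires a pregnancy that starts between day 29 and month 3 to be reported or followed irrespective of causality.

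**Step 4. What is known about exposure.** Protocol 1.4.1 gives a terminal half-life of about 7 hours with little or no accumulation. Five half-lives are 5 × 7 = 35 hours. Twenty-eight days are 28 × 24 / 7 = 96 half-lives.

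**A smaller ambiguity.** The 28-day rule counts pregnancies experienced within the window. It does not say whether one conceived inside the window but found later must be reported.

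**The case against.** The strongest reply is that the two periods serve different purposes. A contraception period may include a precautionary margin, and nothing in the documents says that the reporting window must equal it. On the protocol's own pharmacokinetics, a woman who conceives weeks after stopping has no material exposure, so counting days 29 to 92 the same as days 1 to 28 exaggerates what is missed. Taken over the whole time at issue, the gap also looks smaller. With 52 weeks of dosing (364 days) and M = 91, the reporting window covers (364 + 28)/(364 + 91) = 392/455 = 86%. Finally, this is an exploratory study of 60 subjects, with two methods of contraception and pregnancy tests at every visit, so few late conceptions are likely, although the documents give no rate.

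Most of this stands, and it rules out two stronger conclusions that a reader might draw:
- *That exposed pregnancies and their outcomes are lost to the safety database.* Late exposure is not shown, and a congenital anomaly that is known and judged possibly related is already reportable and followed.
- *That 48 to 54 women are at risk (80% to 90% of 60).* That ratio, from Protocol 1.1, describes systemic sclerosis in general and counts all women. The number of childbearing potential in this trial is not given.

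What the reply does not remove is the mismatch. The sponsor chose 3 months for both sexes and gave no reason for ending the collection of pregnancies sooner. For pregnancy, 9.3.6.1 deliberately sets causality aside. After day 28 the protocol falls back on provisions that depend on it.

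**Conclusion.** The point holds as a low-severity gap in safety capture. About two thirds of the post-dose contraception period (56 to 64 days, 67% to 70%) has no mandatory pregnancy reporting or follow-up regardless of causality.

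The size rests on one assumption, that 3 months means 84 to 92 days. That the 3-month period marks a time of concern about conception is an inference from the contraception and sperm-donation rules read with the animal findings; the protocol does not say so outright. The percentage measures calendar time only. It is not a measure of drug exposure, nor of the number of pregnancies that would be missed.

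**What to change.** Reconcile the two windows in the next amendment, leaving the contraception rules as they are:

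1. In 9.3.6.1, require any pregnancy of a subject or partner, from first dose to the end of the contraception period already set in section 3.4, to be reported within 24 hours of awareness, regardless of relationship. Refer to section 3.4 instead of restating a number, so that the two cannot drift apart. State whether the date of conception or of detection decides.
2. In 6.2.5, and in its repetition in 9.3.6.1, extend follow-up to outcome and to 30 days after delivery to the same pregnancies.
3. At the existing 28-day visit, instruct subjects to report any pregnancy, their own or a partner's, until that period ends.

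This costs about two sentences of protocol text and one instruction, plus a few late reports to process. It adds no visit or test and alters no dose or analysis. Its limit is that, with no scheduled contact after day 28, capture would rely on self-report.

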9.3.6.2 Information to be Provided by the Investigator

[figure not shown]
The SAEs for all enrolled subjects must be recorded on the SAE form (during study participation). This requirement includes all SAEs that occur after informed consent and through **28 days after last dose** of study drug, and in addition, any SAEs that are assessed as possibly related to study drug by the Investigator, even if the SAE occurs more than 28 days after the last dose of study drug must be reported to the Kadmon Corporation Pharmacovigilance Department (or designee).

The minimum information required for SAE reporting includes identity of Investigator, site number, subject number, an event description, SAE term(s), onset date, the reason why the event is considered to be serious (i.e., the seriousness criteria) and the Investigator's assessment of the relationship of the event to study drug. Additional SAE information including medications or other therapeutic measures used to treat the event, action taken with the study drug due to the event, and the outcome/resolution of the event will be recorded on the SAE form. Forms for reporting SAE will be provided to the study sites.

In all cases, the Investigator should continue to monitor the clinical situation and report all material facts relating to the progression or outcome of the SAE. Furthermore, the Investigator may be required to provide supplementary information as requested by the Kadmon Corporation Drug Safety personnel or designee.

When reporting SAEs, the following additional points should be noted:

- When the diagnosis of an SAE is known or suspected, the Investigator should report the diagnosis or syndrome as the primary SAE term, rather than as signs or symptoms. Signs and symptoms may then be described in the event description. For example, dyspnea should not be used as an SAE term if the diagnosis which caused the dyspnea is known to be malignant pleural effusion.
- Death should not be reported as an SAE, but as an outcome of a specific SAE, unless the event preceding the death is unknown. In the exceptional case where the events leading to death are unknown, then death may be used as an event term. If an autopsy was performed, the autopsy report should be provided.
- While most hospitalizations necessitate reporting of an SAE, some hospitalizations do not require SAE reporting, as follows:

- Elective or previously scheduled surgery (e.g., a previously scheduled ventral hernia repair)
- Procedures for pre-existing conditions that have not worsened after initiation of treatment
- o Pre-specified study hospitalizations for observation
- Events that result in hospital stays of less than 24 hours and that do not require admission (e.g., an emergency room visit for hematuria that results in a diagnosis of cystitis and discharge to home on oral antibiotics)
- O SAEs must, however, be reported for any surgical or procedural complication resulting in prolongation of the hospitalization.

9.3.6.3 Regulatory Reporting

Kadmon Corporation Pharmacovigilance Department (or designee) will process and evaluate all SAEs as soon as the reports are received. For each SAE received, Kadmon Corporation will determine whether the criteria for expedited reporting have been met.

Kadmon Corporation (or designee) will submit SAEs that meet the criteria for expedited reporting to the Regulatory Authorities in accordance with local regulations governing safety reporting. Reporting of SAEs by the Investigator to his or her IRB/IEC will be done in accordance with the standard operating procedures and policies of the IRB/IEC. Adequate documentation must be maintained showing that the IRB/IEC was properly notified.

9.4 FOLLOW-UP FOR ADVERSE EVENTS

Any SAE or AE assessed as at least possibly related that led to treatment discontinuation (including clinically significant abnormal laboratory values that meet these criteria) and is ongoing 28 days after last dose of study drug must be followed until either resolution of the event or determination by the Investigator that the event has become stable or irreversible. This follow-up guidance also applies to possibly related SAEs that occur more than 28 days after last dose of study drug. The status of all other continuing AEs will be documented as of 28 days after last dose of study drug.

9.5 OTHER SAFETY CONSIDERATIONS

9.5.1 Laboratory Data

All laboratory data obtained during the course of the study should be reviewed. Any abnormal value that leads to a change in subject management (e.g., dose reduction or delay, requirement for additional medication or monitoring) or is considered to be of clinical significance by the Investigator should be reported as an AE and/or SAE as appropriate, unless this value is consistent with the subject's present disease state or is consistent with values obtained before entry into the study.

Laboratory results will be classified using the CTCAE v5.0.

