6.2.4 Clinical Laboratory Parameters

Clinical laboratory tests will be performed as outlined in the Schedule of Assessments (Appendix A). Samples should be taken pre-dose and will be sent to a central laboratory for analysis (Table 4). Full details for collection and shipping of samples are provided in the Laboratory Manual.

Table 4 Clinical Laboratory Panels

Kadmon Corporation, LLC

Hematology	Serum Chemistry	Other
differential (including at minimum: neutrophils, basophils, eosinophils, lymphocytes, monocytes) Red blood cell count Hemoglobin Hematocrit Platelet count MCV	 Albumin Alkaline phosphatase ALT AST BUN Calcium Chloride CO₂ Creatinine CPK Total and direct bilirubin GGT Globulin Glucose HBV (screening only) HCV (screening only) HIV (screening only) Lactate dehydrogenase Magnesium Phosphorus Potassium Sodium Total protein Uric acid 	Whole blood tuberculin test (screening only)

ALT = alanine aminotransferase; AST = aspartate aminotransferase; BUN = blood urea nitrogen; GGT = gamma-glutamyl transferase; HBV = hepatitis B virus; HCV = hepatitis C virus; HIV = human immunodeficiency virus; MCV = mean corpuscular volume

Abnormalities in clinical laboratory tests that lead to a change in subject management (e.g., dose delay, requirement for additional medication or monitoring) are considered clinically significant for the purposes of this study and will be recorded on the AE eCRF page. Laboratory results will be classified using the CTCAE v5.0. If laboratory values constitute part of an event that meets criteria defining it as serious, the event (and associated laboratory values) must be reported as an SAE (see Section Error! Reference source not found.).

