9. SAFETY

9.1 SAFETY PARAMETERS

Safety data will be collected from the time the subject signs the ICF form until 28 days after their last dose of study drug (the AE reporting period). The primary safety outcome will be the percentage of subjects experiencing AEs in each group.

Safety assessments will include AEs, SAEs, PEs, vital sign measurements, clinical laboratory evaluations (hematology, chemistry, and urinalysis), and ECGs. Reasons for treatment discontinuation because of toxicity will be documented.

All AEs that occur in enrolled subjects during the AE reporting period must be recorded, regardless of the relationship of the AE to study drug. Any known untoward event that occurs beyond the AE reporting period that the Investigator assesses as possibly related to study drug also should be reported to Kadmon.

As this is the first study in subjects with dcSSc, careful monitoring of all toxicities will be carried out. Vital sign measurements, including blood pressure, pulse rate, respiratory rate, and temperature will be monitored throughout the study.

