9.2 ADVERSE EVENT DEFINITION

An AE is defined as any untoward medical occurrence in a clinical trial subject associated with the use of a drug, whether or not considered drug related. An AE can be an unfavorable and unintended sign (e.g., an abnormal laboratory value finding), a symptom, or a disease temporally associated with the use of a drug, without judgment as to causality. An AE can arise from use of the drug (e.g., use in combination with another drug) and from any route of administration, formulation, or dose, including an overdose. An AE also includes, but is not limited to, any clinically significant worsening of a pre-existing condition. Examples include:

- Any sign, symptom, physical finding, or laboratory result that has worsened in nature, severity or frequency compared to baseline
- Reactions from an investigational drug, including those occurring as a result of an overdose, abuse of the study drug, withdrawal phenomena, sensitivity or toxicity
- Concurrent illness that was not present or worsens in nature, severity, or frequency compared to baseline
- Injury or accident and/or

• Exacerbation of a pre-existing condition

For the purpose of data collection, all untoward events that occur after informed consent through 28 days after last dose of study drug are to be recorded on eCRFs by the investigational site.

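### Protocol 9.5.1 waives AE reporting for laboratory values that fit the subject's disease or pre-entry values, while 6.2.4, 9.1 and 9.2 require them to be recorded; one rule is needed

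*Protocol*

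**What the plan says.** Four sections of the protocol govern whether a laboratory abnormality becomes an AE record.

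- **9.5.1 (Laboratory Data)** has two triggers. One is "Any abnormal value that leads to a change in subject management (e.g., dose reduction or delay, requirement for additional medication or monitoring"); the other is the investigator's view that the value is clinically significant. Either leads to an AE or SAE report, "unless this value is consistent with the subject's present disease state or is consistent with values obtained before entry into the study".
- **6.2.4 (Clinical Laboratory Parameters)** uses the first of those triggers and says such abnormalities "are considered clinically significant for the purposes of this study and will be recorded on the AE eCRF page". It has no exemption. It also requires laboratory values that form part of a serious event to be reported as an SAE.
- **9.2 (Adverse Event Definition)** includes "any clinically significant worsening of a pre-existing condition" and gives as an example "Any sign, symptom, physical finding, or laboratory result that has worsened in nature, severity or frequency compared to baseline".
- **9.1 (Safety Parameters)** says that AEs in the reporting period "must be recorded, regardless of the relationship of the AE to study drug".

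On the outcome, 9.1 states: "The primary safety outcome will be the percentage of subjects experiencing AEs in each group". The synopsis gives the same outcome in terms of TEAEs. SAP 3.9.1 defines TEAEs as AEs that occur or worsen after first dose, and has no rule that derives one from laboratory data.

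**The concern.** The exemption in 9.5.1 depends on whether the value fits the disease, so it places a judgement about cause at the recording step. The rest of the protocol makes that judgement after recording. Section 9.3.3 and Appendix F provide a five-level causality scale. Appendix F names disease as an example of an extraneous cause under the not-related category, and makes a ready explanation by the subject's clinical state a criterion for both the unlikely and the possibly related categories. Under 9.5.1, an event that Appendix F could class as possibly drug-related might never be entered.

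The kidney is where this is most plausible. Section 1.1 names it as an organ involved in dcSSc, 3.9 lists renal crisis as an example of disease progression, and 1.3 reports nonclinical findings at or near clinically relevant exposures that include "renal (increased blood urea nitrogen [BUN], tubular changes, pigmentation, intracellular protein droplets in the epithelium"). Drug and disease effects are hard to separate there in a single subject, so a consistent AE record in all arms matters.

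The consequences would be AE, SAE and relatedness tables that omit some events, and different recording of the same value across the roughly 25 centers (3.3). An event that is not recorded also escapes the AE follow-up rule in 9.4.

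**Working it through.** **1. The sections side by side**

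| Laboratory value | 9.5.1 | 6.2.4 | 9.1 and 9.2 |
|---|---|---|---|
| Changed management, worsened from baseline, fits present disease | Exempt | Record | Record |
| Changed management, in line with pre-entry values | Exempt | Record | Generally no conflict, since such a value has usually not worsened |
| Clinically significant, management unchanged, worsened, fits present disease | Exempt | Not addressed | Record |

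In 9.5.1 the exemption follows both triggers and refers back to the abnormal value. It therefore covers values that led to a management change, and it covers SAE as well as AE reporting. The disease-state limb conflicts with 6.2.4, 9.1 and 9.2. The pre-entry limb conflicts mainly with 6.2.4.

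**2. What an omitted record removes, and what survives**

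- Removed: the AE term, its seriousness and its causality, and so its place in the tables by SOC and preferred term, by relationship, for Grade 3 or higher events and for SAEs (SAP 3.9.1).
- Kept: laboratory values and changes by visit and arm, CTCAE shift tables and a listing of Grade 3 or higher results (SAP 3.9.2; Protocol 9.9); dose changes and holds with reasons (SAP 3.7); the primary reason for discontinuation (SAP 3.3; Protocol 14.4).

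**3. Effect on the any-TEAE percentage**

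A subject leaves the numerator only if every TEAE that subject had was exempted. With 20 per group, each such subject moves the group figure by 1/20 = 5 percentage points. The documents do not allow the number of such subjects to be estimated.

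**4. Effect on the protocol's own AE-detection statement**

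Section 9.9 states more than 90% probability of at least one event at a true rate of 14% or more, and more than 80% at 10% or more, with 20 subjects per belumosudil group.

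Formula: P(at least one) = 1 − (1 − p)^n.

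- n = 20, p = 0.14: 1 − 0.86^20 = 95.1%
- n = 20, p = 0.10: 1 − 0.90^20 = 87.8%

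Both stated bounds reproduce. Now let f be the share of a laboratory-only event type left unrecorded under 9.5.1, so that p becomes p(1 − f). **f is an assumption; the documents give no value.**

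| f (assumed) | n = 20, p = 14% | n = 20, p = 10% | n = 40, p = 14% | n = 40, p = 10% |
|---|---|---|---|---|
| 0 | 95.1% | 87.8% | 99.8% | 98.5% |
| 0.10 | 93.2% | 84.8% | 99.5% | 97.7% |
| 0.25 | 89.1% | 79.0% | 98.8% | 95.6% |
| 0.50 | 76.6% | 64.2% | 94.5% | 87.1% |
| 0.75 | 51.0% | 39.7% | 76.0% | 63.7% |

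With n = 20 the stated bounds fail when f exceeds:

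- 1 − (1 − 0.1^(1/20))/0.14 = 1 − 0.1087/0.14 = 0.22 for the 90% bound
- 1 − (1 − 0.2^(1/20))/0.10 = 1 − 0.0773/0.10 = 0.23 for the 80% bound

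With both belumosudil groups pooled (n = 40), the bounds still hold at f = 0.50 and fail at f = 0.75.

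**The case against.** The other side has a good case on consequences, and most of it stands.

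- **The comparison with placebo survives in the laboratory data.** A reader might infer that events treated as disease disappear from any comparison by arm. SAP 3.9.2 and Protocol 9.9 do not support that: a renal imbalance would still show in the summaries and shift tables. The gap is in AE-based tables.
- **Action and reason are captured elsewhere.** Dose-change and discontinuation reasons have their own records and tables, so they are not lost with the AE.
- **The liver.** A reader might extend the point to liver harm. The support is thin: 1.1 does not name the liver as a disease organ, 3.5 excludes liver disease, and 4.12 gives Grade 3 or higher liver tests a dedicated eCRF. Lower-grade changes could in principle be exempted, but no section explains how they would fit dcSSc.
- **The renal route is narrower than it looks.** The exemption concerns this subject's present state, not everything dcSSc can cause. Entry requires creatinine at or below 1.5 × ULN (3.4) and no renal crisis in the preceding 4 months (3.5). Renal crisis is also captured as a discontinuation reason and in CRISS Step 1 (SAP 3.8.1). The renal findings in 1.3 are nonclinical.
- **The dosing scenario.** The tables in 4.12 tie pauses to toxicities, so an investigator who holds drug under them has arguably already called the value a toxicity. The clearer cases are added medication or monitoring. Even so, 9.5.1 itself lists dose reduction and delay among the triggers that its exemption then qualifies.
- **Reading of 9.2.** The phrase that sets causality aside belongs to the general definition, and the bullet on worsened laboratory results is one of its examples. This does not weaken the conflict, because 9.1 separately requires recording regardless of relationship.

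None of this says which rule prevails, and the surviving tables do not restore the term, seriousness or causality of an unrecorded event.

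**Conclusion.** The contradiction stands in the current text: the same laboratory value is exempt under 9.5.1 and reportable under 6.2.4, and the disease-state limb also conflicts with 9.1 and 9.2. Sites can follow either rule in good faith. Because TEAEs come only from AEs, the choice affects the AE, SAE and relatedness tables directly. It affects the any-TEAE percentage only for subjects with no other TEAE.

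The size is not estimable from the documents. The detection figures above are conditional on an assumed f, apply only to events identified by laboratory values alone, and drop below the protocol's stated bounds at f of about 0.22 to 0.23 only on the n = 20 reading. A reader might want to express the harm as a shrunken difference in AE rates between arms; that would need event rates and a waiver share that the documents do not contain, and a rate for one event type would not measure the any-TEAE percentage.

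This is a recording inconsistency worth correcting because the correction is specific and cheap. It does not show that a safety signal would go unseen.

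**What to change.** Reconcile 9.5.1 with 6.2.4, 9.1 and 9.2 so that one AE-recording rule applies at all sites. One way is to confine the exemption in 9.5.1 to values that neither worsened from baseline nor changed subject management. The investigator's view that a value reflects dcSSc then goes in the causality field already collected under 9.3.3 and Appendix F. This concerns recording only and leaves the management rules as they are.

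The SAP could also state how graded laboratory worsening without a matching AE will be handled, for example by a listing from data already planned.

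The cost is a protocol wording change, a site memo and slightly more AE records. No new assessment or data collection is needed.
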